### 1.2 Hypothesis and research questions

#### **Hypothesis:**

In patients with early type 2 diabetes, a short-term intensive metabolic intervention comprising dapagliflozin (Forxiga), metformin, basal insulin glargine and lifestyle approaches will be superior to standard diabetes therapy in achieving sustained diabetes remission.

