**2.2 Secondary objectives**

To determine whether the 12-week metabolic intervention that includes Forxiga is more effective than standard diabetes therapy in achieving diabetes remission and regression when evaluated at 36, 48 and 64 weeks after randomization.

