## **11. STATISTICAL METHODS AND SAMPLE SIZE DETERMINATION**

### **11.1 Proposed sample size and justification**

The sample size calculation is based on the estimated proportion of patients achieving diabetes remission of 10% in the control group. The control group estimate of 10% is based on the proportion of patients in the conventional diabetes treatment group of 13% who achieved FPG < 7.0 mmol/L and HbA1C < 6.2% off therapy after 2 years of follow-up observed in the Dixon *et al.* trial, after adjusting for the longer duration of diabetes since diagnosis in participants in our trial ( $\leq 8$  years versus < 2 years). A total sample size of 152 participants (76 per treatment group) will provide 80% power to show a risk difference of  $\geq 20\%$  in the induction of diabetes remission between treatment groups and 90% power to show a risk difference of  $\geq 23\%$ .

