### **11.2 Statistical analyses**

All group comparisons will be conducted according to the intention-to-treat principle with inclusion of data from all participants according to their treatment group assignment, regardless of adherence to therapy. The primary outcome in this study is the proportion of patients in the intervention group who achieve drug-free diabetes remission 24 weeks after randomization compared to the control group. The treatment groups will be compared using a chi-squared test with  $\alpha = 0.05$  level of significance. The outcome will be reported as a risk difference in the induction of remission between the intervention group and the control group with 95% confidence interval. Any individual who withdraws/drops out prior to the 24, 36, 48 and 64 week visit will be classified as not having achieved drug-free diabetes remission at that point in time. Participants who fail to achieve remission or have hyperglycemia relapse will be censored with respect to diabetes remission outcomes.

For secondary analyses, a chi-squared test will be used for dichotomous outcomes and a two-sample t-test (or a non-parametric equivalent) for continuous outcomes. Secondary outcomes will be used only for generation of new hypotheses. Clinical and metabolic predictors of the successful induction of diabetes remission will be evaluated using logistic regression modeling. We do not plan to perform any interim analyses in this trial.

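### Objective 2.2 sets out to determine superiority in remission at 36, 48 and 64 weeks, but section 11.2 makes every secondary outcome hypothesis-generating; a fixed visit sequence would reconcile the two at no cost to the primary

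*Combined protocol and SAP*

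**What the plan says.** Section 2.2 sets out to determine whether the 12-week intervention "is more effective than standard diabetes therapy in achieving diabetes remission and regression when evaluated at 36, 48 and 64 weeks after randomization". That is two outcomes at three visits, so six comparisons. The hypothesis in section 1.2 is that the intervention "will be superior to standard diabetes therapy in achieving sustained diabetes remission", and the first secondary research question asks about remission at the same three later visits.

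Section 11.2 gives the 24-week remission comparison a chi-squared test at 0.05 and a risk difference "with 95% confidence interval". For dichotomous secondary outcomes it names a chi-squared test, gives no significance level and describes no multiplicity procedure. It then states: "Secondary outcomes will be used only for generation of new hypotheses". No secondary outcome is excepted. Section 5.2.1 mentions key secondary outcomes, but the documents do not list or rank them.

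**The concern.** The objective promises a comparative conclusion that the analysis section does not allow as a confirmatory finding. Durability is the subject of the later visits. Week 24 falls 12 weeks after drugs are stopped at the end of week 12 (section 5.3.3), which is the shortest drug-free period that meets the remission definition. Follow-up continues for a further 64 − 24 = 40 weeks, with three clinic visits (36, 48 and 64 weeks) and seven telephone contacts after week 24 (Appendix A, Table 1).

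If remission still differs clearly at 64 weeks, the plan as written allows the estimate to be reported but treats it as a lead for another trial. The opposite risk lies with a later author or reader who follows the wording of 2.2 and treats the visit-wise tests as confirmatory with no order or adjustment. A testing order fixed in advance would remove both problems.

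**Working it through.** **Inputs from the documents.** Section 11.1: "A total sample size of 152 participants (76 per treatment group"), and an "estimated proportion of patients achieving diabetes remission of 10% in the control group". It claims 80% power for a difference of at least 20 points and 90% for at least 23. Section 11.2: alpha 0.05 for the primary, and no interim analysis. Sidedness is not stated; two-sided is assumed because a 95% interval is planned.

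**Inputs assumed.** The documents give no effect after week 24 and no correlation between visits, so ranges are used for both.

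**1. The plan's own figure.** For a difference d between p1 = 0.10 and p2 = 0.10 + d, with pbar their mean and n = 76 per arm:

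power = Φ{ [d − 1.96·√(2·pbar(1 − pbar)/n)] / √([p1(1 − p1) + p2(1 − p2)]/n) }

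- d = 0.20: (0.20 − 0.1272)/0.0628 = 1.16, so power is 87.7%.
- Subtracting the continuity correction 1/n = 0.0132 from the numerator gives 82.9%. At d = 0.23 the corrected power is 91.1%.
- The corrected formula reaches 80% power at 19.2 points and 90% at 22.5 points. The next whole points are 20 and 23, as stated.

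The sample size is therefore reproduced, and it concerns week 24 only.

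**2. Effect of a fixed sequence on the primary.** Week 24 is tested first, at the full two-sided 0.05, with the same 152 participants. Its power at 10% against 30% is the same with or without the later tests: 87.7% by formula, 89% exact for an uncorrected chi-squared test.

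**3. Familywise error over the four remission tests.** With the sequence, a false claim requires the first true null in the order to be rejected, and that null is tested at 0.05. The error is therefore held at a nominal 5% whatever the correlation (simulated 4.9 to 5.1%). If the four tests were instead read as confirmatory without adjustment:

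| Assumption about visits | Chance of at least one false positive |
|---|---|
| Independent, 1 − 0.95⁴ | 18.5% |
| Latent correlation 0.5 between adjacent visits | about 19% |
| Latent correlation 0.7 | about 18% |
| Latent correlation 0.9 | about 15% |
| Latent correlation 0.98 | about 12% |
| Remission lost and never regained | 9.5 to 11.4% |

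The range is about 10 to 19%. The latent model gives each participant a correlated normal variable at each visit, cut to give the assumed remission rate.

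**4. Chance of a confirmed claim through each visit.** This is the probability that a visit and all earlier ones are significant, with 76 per arm, 10% control remission and an uncorrected chi-squared test:

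| Assumed difference at 24/36/48/64 weeks | Correlation model | 24 | 36 | 48 | 64 |
|---|---|---|---|---|---|
| 20 points throughout | latent 0.7 | 89% | 82% | 75% | 70% |
| 20 points throughout | latent 0.98 | 89% | – | – | 80% |
| 20/16/13/10 points | latent 0.7 | 89% | – | – | 26% |
| 20/16/13/10 points | lost, not regained | 89% | 75% | 59% | 41% |

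The formula in step 1 gives single-visit power of 87.7%, 73.3%, 58.0% and 40.7% at 20, 16, 13 and 10 points. Week-64 power under the fading scenario is thus limited mainly by the small difference; the chain lowers it further when visits are less correlated. In the limiting case where the same people stay in remission throughout and 20 points is sustained, the chain stays at 89%.

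**The case against.** The strongest reply is that the plan made a recognised choice. Confining claims to one primary test and labelling the rest exploratory is a transparent way to handle multiplicity. Section 3.1 calls this a pilot trial, and section 12 looks to future research for refinement. That stands: nothing is wrong with the primary, and a sponsor may keep the exploratory label. It does not remove the mismatch with 2.2. Section 1.1 also describes a pilot already completed and a multicentre trial to follow it, and section 11.1 powers this trial for superiority.

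Three stronger readings are tempting, and the documents do not support them.

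- A reader might infer that objective 2.2 cannot be answered at all. The later visits are still compared by chi-squared test, with dropouts classed as non-remitters, and effects can be estimated. Only an error-controlled claim is missing. Section 2.3 also uses the verb determine for hypoglycemia rates, so it does not by itself mean a confirmatory test.
- A reader might infer that the plan runs uncontrolled tests at 0.05 and so carries an error of 10 to 19%. Section 11.2 ties 0.05 to the primary only, and its hypothesis-generating sentence rules out the confirmatory reading that would produce that error.
- A reader might infer that the hypothesis of sustained remission goes untested. The primary research question defines remission as at least 12 weeks off drugs and assesses it at 24 weeks, so the primary can be read as its test.

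It is also fair to say that later-visit power was never planned, and that regression does not belong in a confirmatory chain. Regression is HbA1C 6.5 to 6.9%, which excludes people in remission. Moving someone from regression into remission lowers the regression rate, so a higher rate is not clearly a benefit.

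**Conclusion.** The concern holds as a mismatch between section 2.2 and section 11.2, together with a missed improvement that costs the primary nothing. It is worth making but does not threaten the trial's main conclusion. As written, no result after week 24 can be confirmatory. With the sequence, the chance of a confirmed claim through week 64 runs from about 26% (difference fading to 10 points, latent correlation 0.7) to about 80% (20 points sustained, latent correlation 0.98). A correlation below 0.7 would lower these figures.

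One part of 11.2 must be settled first. It says that participants who fail to remit or who relapse are censored for remission outcomes. A chi-squared comparison of proportions needs to know whether they count as non-remitters or leave the denominator.

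**What to change.** Before outcome data are seen, replace the hypothesis-generating sentence in section 11.2 with wording such as:

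*Drug-free remission will be tested in the fixed order 24 weeks (primary), 36, 48 and 64 weeks, each at two-sided 0.05. Testing stops at the first non-significant result, and remission at any later visit is then exploratory. All other secondary outcomes are exploratory. At each visit every randomised participant stays in the denominator, and those who did not remit or who have relapsed count as not in remission.*

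The last sentence replaces the one on censoring. Reword 2.2 so that regression is described as exploratory. If the sponsor prefers not to adopt the sequence, reword all of 2.2 as exploratory so that it agrees with 11.2; the censoring sentence should be clarified either way.

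The cost is a few sentences, with no added participants, visits or primary alpha. The downside is that a later visit cannot be claimed if an earlier one fails, and the sample size was not chosen for the later visits.

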## **12. SIGNIFICANCE**

This trial builds on our ongoing pilot trial and other trials to identify a menu of metabolic remission strategies that can then be refined and tailored to individual needs based on future

research. Such an approach represents a fresh innovative approach that could turn the therapy of type 2 diabetes from a lifelong burden of drugs to either one-time or intermittent remission-induction courses that may translate into better overall quality of life and health-related outcomes.

### 13. APPENDIX A

**Table 1.** Schedule of visits and assessments in the intervention group (I), control group (C), and both groups (X).

	Weeks after randomization																			
	-1	0	0.5	1	1.5	2	2.5	3	3.5	4	4.5	5	5.5	6	7	8	9	10	11	12
Eligibility criteria	X																			
Informed consent	X																			
Randomization		X																		
Start study medications		I																		
Stop diabetes medications																				X
Clinic visit	X	X		I		I		I		I		I		X		I		I		X
Telephone follow-up			I		I		I		I		I		I		I		I		I	
Adherence to medications and side effects			I	I	I	I	I	I	I	I	I	I	I	X	I	I	I	I	I	X
Review SMBGs			I	I	I	I	I	I	I	I	I	I	I	X	I	I	I	I	I	X
Height	X																			
Weight	X	X						I						X		I		I		X
Waist and Hip Circumference		X												X						X
Blood pressure	X	X		I		I		I		I		I		X		I		I		X
Physical activity and food frequency questionnaires*	X																			X
ECG	X																			
Fasting serum for storage**	X																			
FPG	X																			
Serum ALT	X																			
Serum creatinine	X					I								I				I		
Urine BhCG***	X																			
HbA1C	X																			X
Two glucose profiles****														X						X
Return to standard glycemic care if hyperglycemia relapse identified																				
AE/SAE Review and Reporting			X	X	X	X	X	X	X	X	X	X	X	X	X	X	X	X	X	X

\*A quality of life questionnaire will also be administered at -1, 12 and 64 weeks.

\*\*Fasting serum sample will be taken for storage during the screening visit and at 16 weeks.

\*\*\*Urine BhCG will be measured in women with childbearing potential.

\*\*\*\* Two six-point glucose profiles will be collected on separate days. Each six-point glucose profile will include pre-meal and 2-hour post-meal SMBG readings taken on the same day.

	Weeks after randomization													
	12.5	16	20	24	28	32	36	40	44	48	52	56	60	64
Eligibility criteria														
Informed consent														
Randomization														
Start study medications														
Stop diabetes medications														
Clinic visit		X		X			X			X				X
Telephone follow-up	X		X		X	X		X	X		X	X	X	
Adherence to medications and side effects	X	X	X	X	X	X	X	X	X	X	X	X	X	X
Review SMBGs	X	X	X	X	X	X	X	X	X	X	X	X	X	X
Height														
Weight		X		X			X			X				X
Waist and Hip Circumference		X		X			X			X				X
Blood pressure		X		X			X			X				X
Physical activity and food frequency questionnaires*				X			X			X				X
ECG														
Fasting serum for storage**		X												
FPG		X												
Serum ALT		X												X
Serum creatinine		X												X
Urine BhCG***														
HbA1C				X			X			X				X
Two glucose profiles****														
Return to standard glycemic care if hyperglycemia relapse identified	X	X	X	X	X	X	X	X	X	X	X	X	X	X
AE/SAE Review and Reporting	X	X	X	X	X	X	X	X	X	X	X	X	X	X

\*A quality of life questionnaire will also be administered at -1, 12 and 64 weeks.

\*\*Fasting serum sample will be taken for storage during the screening visit and at 16 weeks.

\*\*\*Urine BhCG will be measured in women with childbearing potential.

\*\*\*\* Two six-point glucose profiles will be collected on separate days. Each six-point glucose profile will include pre-meal and 2-hour post-meal SMBG readings taken on the same day.
